2.1. Study Design

This is a multicenter, 6-week, open-label, single-arm study to demonstrate the safety and characterize the pharmacokinetics of PF-06412528 in children 7 to 17 years of age, with moderate-to-severe chronic pain requiring continuous around-the-clock therapy with an opioid analgesic for an extended period of time. The study consists of 4 study periods (Figure 1) including:

- *Screening Period (Visit 1) lasting up to 2 weeks.*
- *Treatment Period (Visits 2-6) lasting up to 10 weeks.*
- *Post-Treatment Period (Visit 7) lasting 1 week.*
- *End of Study Period (Visit 8) lasting 3 weeks.*

Figure 1. Overall Study Design

The study will enroll approximately 140 children between the ages of 7 and 17 years with at least 100 subjects completing the Maintenance Phase. Plasma samples will be collected at 2 time points under steady-state conditions from each subject in the two age groups (7-11 years and 12-17 years) to characterize the pharmacokinetics of morphine and determine the systemic exposures of naltrexone and 6- β -naltrexol.

The Screening Period occurs up to 2 weeks. This period includes one scheduled study center visit.

The Treatment Period of the study will be conducted using an open-label, non-randomized, single-arm study design to demonstrate the safety and characterize the pharmacokinetics of PF-06412528 under multiple dose conditions. The Treatment Period occurs over 10 weeks and consists of two phases of variable lengths depending on when a subject achieves a stable dose of PF-06412528; a Conversion/Titration Phase lasting 1-4 weeks and a Maintenance Phase lasting 6 weeks. A stable dose is characterized as a dose that provides adequate analgesia and minimizes adverse reactions over a 5 to 7-day period. The purpose of the Conversion/Titration Phase is to convert subjects from their current opioid therapy to PF-06412528 using a standardized conversion guide..., and individualize subjects' pain management by titrating with PF-06412528. The purpose of the Maintenance Phase is to maintain the subject on a stable dose of PF-06412528 for an additional 6 weeks, such that a subject could potentially be exposed to up to 10 weeks of treatment with PF-06412528.

Blood samples will be collected for pharmacokinetic analysis at Visit 4 only for those subjects that achieve a stable dose between Visits 3a-d. Two blood samples will be taken two-hours apart at Visit 4. Subjects will be assigned 1:1 with respect to beginning the pharmacokinetic sampling within either 0-to-5 hours or >5 to \leq 9 hours after the morning dose of PF-06412528. Only the first of the two pharmacokinetic samples must be collected within the designated time window; the other sample should be collected approximately two hours after the first sample.

The purpose of the Post-Treatment Period (Visit 7) is to perform safety assessments 7 \pm 2 days after the last dose of PF-06412528. All treated subjects will be required to attend Visit 7, including those who discontinued early.

The purpose of the End of Study Period (Visit 8) is to perform final safety assessments 28 \pm 2 days after the last dose of PF-06412528 for all treated subjects. This visit may be performed as an in-clinic visit or by telephone.

2.2. Study Objectives

2.2.1. Primary Objectives

- To demonstrate the safety of PF-06412528 in children 7 to 17 years of age treated with PF-06412528 for chronic, moderate-to-severe pain.*
- To characterize the pharmacokinetics of morphine in children 7 to 17 years of age treated with PF-06412528 for chronic, moderate-to-severe pain.*

2.2.2. Secondary Objectives

- *To determine the exposures of naltrexone and 6- β -naltrexol in children 7 to 17 years of age treated with PF-06412528 for chronic, moderate-to-severe pain.*

3. INTERIM ANALYSES, FINAL ANALYSES AND UNBLINDING

No interim analysis is planned. Final analysis will follow the official database release. Since this is an open label single-arm study, unblinding is not applicable.

With respect to pharmacokinetics, it is estimated that a sample size of N=50 per treatment group would provide adequate (>80%) power to estimate CL/F and Vd/F, taking into consideration the sample size estimates for various levels of PK variability as described by Wang, et al. However, since the study is expected to enroll slowly over time, modeling and simulation will be performed - beginning with adult population PK model and adding pediatric data from each age group as it becomes available – to verify that the sample size and the sampling scheme proposed for the present study are adequate to estimate CL/F and Vd/F with 80% power to establish the 95% CI within 60 to 140% of the geometric mean value for each PK parameter.

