#### **5.4.** Administration

PF-06412528 is to be administered with or without food, as per the investigator's Brochure. The bottle label will direct the subject to take either QD or BID depending on the total daily dose requirement for that subject (eg, children of low weight may be assessed to start with the 10 or 15 mg dose QD. Those labels will indicate QD dosing. Dosing strengths greater than 15 mg will indicate BID dosing). When given BID, one dose must be administered in the morning and the second dose is to be administered approximately 12 hours later. Morning doses should be encouraged to be administered daily between 6:00-10:00 AM throughout the study. As a general rule, the initial calculated daily dosage of PF-06412528 should be reduced by 50% and then titrated to achieve a stable dose. When converting to PF-06412528, the investigator should consider the potency, route of administration, and total daily dose of the discontinued opioid(s), the medical status of the subject, the subject's degree of opioid experience and tolerance, the type and severity of chronic pain, and the use of concomitant rescue medications to control the pain. Because

steady-state plasma concentrations are approximated within 24 to 36 hours, PF-06412528 dosage adjustments may be done as frequently as every 1 to 2 days. Study drug will be dispensed to the subject's caregiver only.

When PF-06412528 extended-release capsules are administered whole, the naltrexone remains intact and does not affect the analgesic potential of morphine. However, if the capsule is crushed, chewed or dissolved, the naltrexone component is released, competitively binds at the mu-opioid receptors, thus inhibits the effects of the opioid.

Therefore, PF-06412528 extended-release capsules are to be swallowed whole. The pellets in the capsules are not to be crushed, chewed, or dissolved prior to swallowing.

The co-ingestion of PF-06412528 with alcohol could result in an increase in morphine plasma levels and potentially fatal overdose of morphine. Subjects should not consume alcoholic beverages or use prescription or non-prescription products containing alcohol while on PF-06412528 therapy.

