#### 9.3.3. Pharmacokinetic Analysis

Given the expected very low fluctuation in steady-state morphine concentrations following PF-06412528 BID dosing in children based on PF-06412528 study ALO-KNT-202 in adults, the concentrations observed during the maintenance phase will be used as an estimate of  $C_{ss,av}$  of morphine and its metabolites (data permitting) in pediatric subjects. The CL/F of morphine will be estimated using a ratio of the daily dosing rate of PF-06412528 and the estimates of morphine  $C_{ss,av}$  in the Maintenance Phase. The concentration-time dataset will be analyzed to obtain estimates for Vz/F of morphine in pediatric subjects, data permitting. Covariates of interest (PF-06412528 dosage, age, body weight, gender, concomitant medications etc) will be assessed for their ability to account for the observed variability in morphine  $C_{ss,av}$ .

The observational data will be summarized using descriptive statistics (mean, standard deviation, median, minimum, and maximum) for the study group as a whole. Data permitting, graphical representations and regression analyses may be used to characterize the dose-exposure relationships for morphine, naltrexone, and 6-β-naltrexol.

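### SAP 3 estimates more than 80% power at N=50 for morphine Vd/F, but on the near-flat profile the protocol relies on, the children's two samples do not support that figure; for CL/F they do.

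*SAP*

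**What the plan says.** SAP 3 states that "it is estimated that a sample size of N=50 per treatment group would provide adequate (>80%) power to estimate CL/F and Vd/F". The stated basis is "taking into consideration the sample size estimates for various levels of PK variability", with a citation to a paper on precision criteria for paediatric PK studies. Its next sentence plans modelling and simulation to confirm that sample size and sampling scheme give "80% power to establish the 95% CI within 60 to 140% of the geometric mean value for each PK parameter". SAP 6.2.1.1 lists CL/F and Vd/F as the primary PK endpoints.

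On sampling, SAP 2.1 says "Two blood samples will be taken two-hours apart at Visit 4" and "Subjects will be assigned 1:1 with respect to beginning the pharmacokinetic sampling within either 0-to-5 hours", or between 5 and 9 hours, after the morning dose. SAP 8.2.2 starts from a one-compartment model with first-order absorption. It allows full adult data to be added, or the absorption parameters to be fixed.

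The current protocol differs. Protocol 2.2.1 and 9.3.2 make CL/F and Css,av primary. Protocol 2.2.2 and 9.3.2 make Vz/F secondary, to be estimated only if the data allow. Protocol 9.3.3 uses observed concentrations as estimates of Css,av, "Given the expected very low fluctuation in steady-state morphine concentrations following PF-06412528 BID dosing in children". The Document History, explaining Amendment 2, gives low fluctuation and sparse sampling as the reasons for removing volume from the primary endpoints.

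**The concern.** At steady state the average concentration is fixed by dose rate and CL/F. Volume shows only in the rise and fall within a dosing interval. The flatter the profile, the better one sample stands in for Css,av and the less any pair of samples says about volume. The protocol relies on the first consequence, while SAP 3 makes a precision claim that the second works against. A sample size indexed only by between-child variability does not show this, because it carries no term for the sampling scheme.

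At stake is how a paediatric volume would be read. Under the SAP's wording it would look adequately powered from children, although its precision might come mainly from fixed absorption parameters or adult data. The planned simulation check would also be judging the design against a volume criterion that it is unlikely to meet on a near-flat profile.

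**Working it through.** **1. The target.** For a CI symmetric on the log scale, the upper limit binds: ln 1.4 = 0.336, against -ln 0.6 = 0.511 below. So SE(ln V) must be at most 0.336/1.96 = 0.172. An expected SE exactly at that limit gives only about an even chance of success; 80% power needs a smaller one.

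**2. The SAP's figure.** No CV is given, so it cannot be reproduced exactly. If each child's parameter were observed directly, power would be P(t(0.975, n-1)·s/√n ≤ ln 1.4), with σ² = ln(1+CV²). At n = 50 this is about 100% for CV 30 to 100%, 99% at 120%, 83% at 150% and 59% at 170%. A figure above 80% therefore agrees with the criterion up to a CV of about 150%, provided that sampling costs no information.

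**3. The sampled design.**

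From the documents:
- CL/F 23.1 mL/min/kg (1.386 L/h/kg) and V/F 5.2 L/kg (Protocol 1.3), so ke = 1.386/5.2 = 0.267/h.
- BID dosing (τ = 12 h), the SAP's two windows, a 2 h gap and N = 50.

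Assumed:
- ka known exactly and the same in every child, which favours the plan.
- Between-child log-SD 0.3 for CL and for V.
- Residual error 10, 20 and 30%.
- Protocol 5.4 says "steady-state plasma concentrations are approximated within 24 to 36 hours". Taking this as 3.3 to 5 half-lives gives 36/3.3 = 10.9 h down to 24/5 = 4.8 h, so ka = ln 2/half-life is about 0.064 to 0.14/h. The table goes beyond this range on both sides.

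Model: C(t) = D·ka/[V(ka-ke)] × [e^(-ke·t)/(1-e^(-ke·τ)) - e^(-ka·t)/(1-e^(-ka·τ))]. With J the derivatives of ln C at the two times with respect to ln CL and ln V, the information is Σ Jᵀ(ω²JJᵀ+σ²I)⁻¹J. The SEs come from its inverse.

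| ka (/h) | Peak/trough | SE(ln V), 10% error | 20% | 30% |
|---|---|---|---|---|
| 0.05 | 1.24 | 0.356 | 0.619 | 0.825 |
| 0.064 | 1.32 | 0.283 | 0.486 | 0.646 |
| 0.087 | 1.46 | 0.214 | 0.362 | 0.478 |
| 0.10 | 1.55 | 0.190 | 0.318 | 0.417 |
| 0.14 | 1.84 | 0.145 | 0.234 | 0.305 |
| 0.22 | 2.58 | 0.106 | 0.163 | 0.207 |

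SE(ln CL) is 0.04 to 0.05 throughout. With log-SD 0.5 it is 0.07 to 0.08, and SE(ln V) is larger: 0.42 to 1.06 at peak/trough 1.21. Over ratios of about 1.2 to 1.55 the range is thus about 0.2 to 1.1, and it grows as the profile flattens. If ka is estimated from the children's data, SE(ln V) is about 0.7 or more.

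**4. Simulated power at N = 50, ka fixed at its true value.**
- 120 trials per cell, Wald intervals, 20% error: 0% at peak/trough 1.24, 0% at 1.46, 11% at 1.92 and 83% at 3.5. With 10% error: 28% at 1.46. CL/F: 100% in every cell.
- 60 trials per cell, profile likelihood, 10% error: 0% at ka 0.064, 12% at 0.10 and 62% at 0.14. With 20 or 30% error: 0% at all three.
- Pooling to N = 100 with 20% error: 0% at 1.46 and 56% at 1.92.

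The table is somewhat optimistic. At peak/trough 1.46 with 10% error, the simulated estimates of ln V had an SD of 0.33, against a median reported SE of 0.21.

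**The case against.** Five points deserve weight.

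- **The figure is provisional.** SAP 3 calls it an estimate and commits to checking sample size and sampling scheme by simulation. That stands, and it limits the criticism to the figure as now stated. It does not support the figure, and the planned check keeps the same volume criterion.
- **The inputs are assumed.** ka, between-child SD and residual error are not in the documents, and part of Protocol 9.1 is blacked out. That stands: the result is a range. The 60-trial cells are also imprecise; 62% has a 95% CI of about 48 to 74%.
- **The documents allow kinder conditions.** Protocol 5.3.1 includes QD regimens, and Protocol 7.5.1 asks for samples at least 2 hours apart. At 10% error, an assumed 25% of children on QD gives SE(ln V) of about 0.15 at ka 0.10 and 0.12 at ka 0.14. A 4 h gap, all BID, gives 0.135 and 0.103. These are inside the limit, so 62% is not a ceiling. At 20% error, both variations still miss the limit at ka 0.10 and below.
- **Adult data may be used.** SAP 3 begins from an adult model and SAP 8.2.2 allows enrichment. No calculation here includes adult data, and they could narrow the interval. That precision would then come from adults and assumed scaling, not from 50 children.
- **The sponsor has already moved.** The protocol demoted volume for this very reason, so the SAP sentence looks like text that was not updated. That makes the correction easier but does not remove the claim.

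A reader might also infer that the cited paper's method ignores sparse sampling, or that the sponsor miscalculated. The documents do not show that method, and SAP 3 says only that such estimates were considered.

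**Conclusion.** The concern holds in a conditional form. On a near-flat profile (peak/trough up to about 1.55), two samples 2 hours apart from 50 children on BID dosing give SE(ln V) of about 0.2 to 1.1, against the 0.17 needed. Simulated power in that region is 0 to 28%. CL/F meets the criterion easily. The result rests on the published paediatric CL/F and V in Protocol 1.3, a known ka, log-SD 0.3 to 0.5 and residual error of 10 to 30%.

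It would be tempting to conclude that the study can never have 80% power for volume. The documents do not support that. The expected SE falls below the limit with 10% error plus a QD share, a longer gap or peak/trough of about 1.8 or more, and with higher error if fluctuation is clearly larger (83% power at 3.5 with 20% error). But clearly larger fluctuation would undercut the protocol's use of observed concentrations as Css,av.

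Harm is limited: the trial has no hypothesis or decision rule, and volume is no longer primary in the protocol. The correction should still be made, because the SAP states a power that its basis does not establish for volume.

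**What to change.** In SAP 3, limit both power sentences and the 60-140% criterion to CL/F. Align SAP 6.2.1.1 with Protocol 2.2 and 9.3.2: CL/F and Css,av primary, Vz/F secondary and only if the data allow. Wherever Vz/F is reported, state that it is not powered, give its relative standard error, and say whether ka and Tlag were fixed or adult data were added.

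This changes SAP wording only and adds no patients, samples or visits. The one downside is that a favourable power statement for volume is withdrawn.

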4. HYPOTHESES AND DECISION RULES

4.1. Statistical Hypotheses

Since this is open label single arm study, no statistical hypothesis is proposed.

4.2. Statistical Decision Rules

Not Applicable.

5. ANALYSIS SETS

5.1. Safety Analysis Set

One safety population is planned consisting of all subjects who participate in the Treatment Period and receive at least one dose of PF-06412528.

5.2. Pharmacokinetic (PK) Analysis Set

The pharmacokinetic concentration population will be defined as all subjects who have undergone at least 1 plasma concentration measurement in this study. The pharmacokinetic analysis population will be defined as all pediatric subjects who have usable pharmacokinetic data (ie, data for which the relationship between the time of dose time of sampling can be determined) and are included in the estimates of the primary pharmacokinetic parameters of interest.

5.3. Treatment Misallocations

All analyses will be performed on an “as-treated” basis. Subjects receiving a treatment that is not consistent with the treatment they are intended to receive will be reported under the treatment that they actually received for all safety and PK analyses, where applicable.

5.4. Protocol Deviations

Subjects who experience events that may affect their PK profile (eg, lack of compliance with dosing) may be excluded from the PK analysis. At the discretion of the pharmacokineticist/clinical pharmacologist, a concentration value may also be excluded if the last dose time prior to PK sampling is not recorded or if the concentration is anomalous for any other reason.

A full list of protocol deviations will be compiled and reviewed to identify major and minor deviations prior to database closure.

6. ENDPOINTS AND COVARIATES

6.1. Safety Endpoints

6.1.1. Primary

Incidence, intensity, relationship, and seriousness of adverse events (including symptoms of opioid toxicity or withdrawal) during treatment with PF-06412528.

6.1.2. Secondary

Changes in vital signs (pulse rate, blood pressure, respiratory rate), clinical chemistry, and hematology laboratory values.

Additional safety data includes:

- Electrocardiogram
- Clinical opiate withdrawal scale (COWS)
- Physical examination
- Urine drug test
- Columbia- Suicide Severity Rating Scale (C-SSRS)

6.2. Pharmacokinetics/Pharmacodynamics Endpoints

[figure not shown]
6.2.1. PK Endpoints

6.2.1.1. Primary

population pharmacokinetic estimates of morphine apparent clearance (CL/F) and volume of distribution (Vd/F) following treatment with PF-06412528

6.2.1.2. Secondary

exposure levels of the metabolites of morphine (morphine-3-glucuronide [M3G] and morphine-6-glucuronide [M6G]), naltrexone, and 6-β-naltrexol following multiple-dose treatment with PF-06412528.

CCI

6.2.2. PD Endpoints

Not applicable

6.3. Efficacy Endpoints

- *Pain intensity scores*
- *Rescue medication or additional analgesic medication use*

6.4. Covariates

Covariate testing will be done by adding continuous (age, body weight) and categorical (gender) variables to the structural PK model to improve fit and reduce variability.

7. HANDLING OF MISSING VALUES

For the analysis of safety endpoints, the sponsor data standard rules for imputation will be applied.

7.1. Concentrations Below the Limit of Quantification

In all data presentations (except listings), concentrations below the limit of quantification (BLQ) will be set to zero. (In listings BLQ values will be reported as “<LLQ”, where LLQ will be replaced with the value for the lower limit of quantification.)

7.2. Deviations, Missing Concentrations and Anomalous Values

In summary tables and plots of median profiles, statistics will be calculated having set concentrations to missing if 1 of the following cases is true:

1. A concentration has been collected as ND (ie not done) or NS (ie no sample),
2. A deviation in sampling time is of sufficient concern or a concentration has been flagged anomalous by the pharmacokineticist.

Note that summary statistics will not be presented at a particular time point if more than 50% of the data are missing.

7.3. Pharmacokinetic parameters

Actual PK sampling times will be used in the population PK analysis.

If an individual subject has a known biased estimate in PK concentrations (due for example to an unexpected event such as vomiting before all the drug is absorbed in the body), this will be footnoted in summary tables and will not be included in population PK analyses.

8. STATISTICAL METHODOLOGY AND STATISTICAL ANALYSES

8.1. Safety Analysis

For the analysis of safety endpoints, the sponsor data standard rules for reporting will be applied.

8.1.1. Treatment and Disposition of Subjects

Subject evaluation groups will show end of study subject disposition and will show which subjects were analyzed for pharmacokinetics and safety (adverse events and laboratory data). Frequency counts will be supplied for subject discontinuation(s) by phase.

8.1.2. Demographic and Clinical Examination Data

A breakdown of demographic data will be provided for age, race, weight, body mass index, and height. Each will be summarized by sex at birth and 'All Subjects' in accordance with the sponsor reporting standards.

8.1.3. Discontinuation(s)

Subject discontinuations, temporary discontinuations or dose reductions due to adverse events will be detailed and summarized.

8.1.4. Adverse Events

All AEs will be coded to System Organ Class and Preferred Term (using MedDRA®). Treatment-emergent AEs will be defined as AEs that commence on or after the start of PF-06412528 administration. Subjects who have multiple events in the same System Organ Class and Preferred Term in a period will be counted only once at each level of summation (overall, by System Organ Class, and by Preferred Term).

Treatment-emergent AEs will be summarized separately for the Conversion/Titration Phase and the Maintenance Phase (including up to End of Study) by System Organ Class, Preferred Term, maximum intensity, and highest relationship to study drug.

Serious AEs and those leading to study discontinuation will be summarized.

8.1.5. Laboratory Data

Clinical laboratory data (hematology, chemistry and urinalysis) including changes from Screening will be summarized descriptively by study visit, as applicable.

8.1.6. Electrocardiogram

Electrocardiogram data including changes from Screening will be summarized descriptively by study visit, as applicable.

8.1.7. Vital Signs

Vital signs data including changes from Baseline will be summarized descriptively by study visit, as applicable.

8.1.8. Opiate Withdrawal

COWS scores will be summarized descriptively by study visit, as applicable. Additionally, for COWS, the proportion of subjects with mild (COWS Score 5-12), moderate (COWS Score 13-24), moderately severe (COWS Score 25-36), or severe withdrawal (COWS Score >36) will be presented.

8.1.9. Columbia-Suicide Severity Rating Scale

Responses to the C-SSRS will be summarized descriptively.

